7 STUDY DESIGN

[figure not shown]
7.1 Overall Design

This is a Phase 3, 2-part (Parts A and B), multicenter study evaluating the PK, safety, and tolerability of ELX/TEZ/IVA TC therapy in CF (F/F and F/MF genotypes) subjects 6 through 11 years of age (inclusive).

Part A

A schematic of the study design for Part A is provided in Figure 7-1. Approximately 12 subjects (F/F or F/MF genotypes) are planned for enrollment. During the Treatment Period, subjects will be administered ELX/TEZ/IVA for approximately 15 days. A review of safety, tolerability, and available PK data will be completed by an internal Vertex team after Part A to confirm or adjust the dose(s) chosen for Part B. Additional subjects may be enrolled as needed in Part A, based on emerging PK data, to confirm the dose(s) for Part B. Subjects who participate in Part A may participate in Part B.

Figure 7-1 Part A Study Design

IVA: ivacaftor; n: number of subjects; TEZ: tezacaftor

^a VX-445/TEZ/IVA will be administered from Day 1 through Day 15. On Day 15, only the morning dose will be administered.

[figure not shown]
Part B

A schematic of the study design for Part B is provided in Figure 7-2. Part B will initiate after completion of the internal Vertex team's review of available data in Part A that will confirm or adjust the dose(s) to be evaluated in Part B. Approximately 56 subjects (F/F or F/MF genotypes) are planned for enrollment to ensure approximately 45 subjects complete Part B. Approximately 25 subjects with F/MF genotypes and approximately 20 subjects with F/F genotypes are targeted for enrollment in Part B. During the Treatment Period, subjects will be administered ELX/TEZ/IVA for approximately 24 weeks.

Subjects who complete the Part B Treatment Period and have not permanently discontinued study drug will be offered the opportunity to enroll in an optional open-label extension safety study (enrollment will be based on the eligibility criteria specified within the Open-label Extension Safety Study protocol).

Figure 7-2 Part B Study Design

IVA: ivacaftor; TEZ: tezacaftor

- ^a The Safety Follow-up Visit is scheduled to occur 4 weeks (± 7 days) after the last dose. This visit is not required for subjects who enroll in an optional open-label extension safety study within 28 days of the last dose.
- ^b Subjects who complete the visits in the Treatment Period, regardless of whether they are on a treatment interruption, will be offered the opportunity to enroll in an optional open-label extension safety study evaluating VX-445 in a triple combination regimen.

The planned dosages to be evaluated are shown in [Table 7-1](#).

Table 7-1 Part A and Part B Doses

Subjects Weight	ELX Dose	TEZ Dose	IVA Dose
Part A			
All subjects	100 mg qd	50 mg qd	75 mg q12h
Part B			
<30 kg	100 mg qd	50 mg qd	75 mg q12h
≥ 30 kg	200 mg qd	100 mg qd	150 mg q12h

ELX: elexacaftor; IVA: ivacaftor; qd: daily; q12h: every 12 hours; TEZ: tezacaftor

7.2 Sample Size and Power

Part A

Approximately 12 subjects will be enrolled in Part A. Sample size calculations were determined based on ELX PK, using noncompartmental analysis (NCA)-based parameters, such as clearance and volume of distribution. Based on the variability observed in adults, data from 12 subjects will allow

80% power to target a 95% CI within 60% and 140% of the geometric mean estimate of clearance for ELX.

Part B

The planned enrollment is approximately 56 subjects. Approximately 45 subjects are expected to complete Part B. Incidence of AEs is a safety endpoint. Table 7-2 presents estimates of the probability for observing at least 1 subject with an AE for the given incidence (θ) and sample size. The study will have at least 90% chance of observing an AE in at least 1 subject if the true incidence rate is 5%; and a >95% chance of observing an AE in at least 1 subject if the true incidence rate is 10%. The probabilities have been calculated by assuming a binomial distribution for the number of AEs using SAS.

Table 7-2 Probability of Observing At Least 1 Subject with an AE in the Study if the AE Incidence (θ) is 5% and 10%

Sample Size	$\theta = 5\%$	$\theta = 10\%$
45	90.0%	99.1%
50	92.3%	99.5%

AE: adverse event

7.3 Randomization

Part A and Part B

Randomization is not relevant (open-label study).

7.4 Blinding and Unblinding

Part A and Part B

This is an open-label study. Refer to Section 10.7 of the CSP for details.

8 ANALYSIS SETS

Part A and Part B

The analysis set will be defined separately for Part A and Part B.

8.1 All Subjects Set

The **All Subjects Set** will include all subjects who are enrolled or receive at least 1 dose of study drug. This analysis set will be used for all individual subject data listings and disposition summary tables, unless otherwise specified.

8.2 Safety Set

The **Safety Set** will include all subjects who receive at least 1 dose of study drug. The Safety Set will be used for all safety analyses.

8.3 Full Analysis Set

The **Full Analysis Set (FAS)** will include all subjects who are enrolled and carry the intended *CFTR* allele mutation and receive at least 1 dose of study drug. The FAS will be used to summarize subject demographics and baseline characteristics, and for analyses of all efficacy and PD endpoints, unless otherwise specified.

9 STATISTICAL ANALYSIS

9.1 General Considerations

Part A and Part B

Data from Part A and Part B will be analyzed separately.

The Schedule of Assessments is provided in Section 3 of the CSP. The precision standards for reporting safety and efficacy variables are provided in an internal Biometrics document that specifies the programming rules including the precision for derived variables.

Continuous variables will be summarized using the following descriptive summary statistics: the number of subjects (n), mean, standard deviation (SD), median, minimum value (min), and maximum value (max).

Categorical variables will be summarized using counts and percentages. Percentages will be presented to 1 decimal place.

Baseline unless otherwise specified, is defined as the most recent non-missing measurement (scheduled or unscheduled) collected prior to the first dose of study drug in the corresponding Part.

Note: for subjects who take Orkambi or Symdeko (branded as Symkevi in Europe) during the 28 days before the screening visit, the data collected at screening visit will not be used for baseline derivation for spirometry, sweat chloride and LCI.

Absolute change from baseline will be calculated as Post-baseline value – Baseline value.

Relative change from baseline will be calculated and expressed in percentage as 100% × (Post-baseline value – Baseline value) / Baseline value.

Treatment-emergent (TE) Period for Part A and Part B will include the time from the first dose of study drug in the corresponding Part through 28 days after the last dose or the completion of study participation date in the corresponding Part, whichever occurs first.

Extended Treatment-emergent (TE) Period for Part B will include the time from the first dose of study drug in Part B through the completion of study participation.

For subjects who do not have unscheduled visit after the Week 24 visit, refer to Section 9.1.6 of the CSP for the definition of completion of study participation. For subjects who have unscheduled visit after the Week 24 visit, the completion of study participation is defined as the date of the last unscheduled visit.

Unscheduled visits: Unscheduled visit measurements will be included in analysis as follows:

- In scheduled visit windows per specified visit windowing rules

- In the derivation of baseline and last on-treatment measurements
- In the derivation of maximum and minimum values during TE periods, and maximum and minimum change from baseline values during TE periods for safety analyses
- In individual subject data listings as appropriate

Visit windowing rules: For analysis specified in Sections 9.2, 9.3, and 9.4, the analysis visit windows for protocol-defined visits are provided in [Appendix A](#).

Incomplete/missing data will not be imputed, unless specified otherwise.

Outliers: No formal statistical analyses will be performed to detect or remedy the presence of statistical outliers, unless specified otherwise.

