**Table 3-4 VX18-445-106, Part B Treatment Period and Safety Follow-up Visit**

Event/ Assessment a	Day 1	Day 3 (± 1 day)	Day 15 (± 3 days)	Week 4 (± 5 days)	Week 8 (± 5 days)	Week 12 (± 5 days)	Week 16 (± 5 days)	Week 20 (± 5 days)	Week 24 (± 5 days)	ETT Visit	Safety Follow-up Visit 28 (± 7) Days After the Last Dose of Study Drug b	Comments
Clinic Visit	X		X	X	X	X	X		X	X	X	
Telephone Contact		X						X				Assess the subject's status, any AEs, concomitant medications, treatments, and procedures.
Inclusion and Exclusion Criteria Review	X											Section 8 for details
Safety and Efficacy Assessments												
CFQ-R	X			X	X	X	X		X	X	X	Completed before the start of any other assessments (Section 11.4.5).
Modified Facial Hedonic Scale	X		X	X	X	X	X		X	X	X	Completed immediately after dosing with study drug (Section 11.3.1).
Ophthalmologic Examination									X at or up to 4 weeks before	X		Section 11.5.5
Full Physical Examination	X					X			X	X		Section 11.5.3 for details. Symptom-directed physical examinations will occur at any time during the study if deemed necessary by the investigator.
Weight, Height, and BMI	X		X	X	X	X	X		X	X	X	Weight and height will be measured before study drug dosing with shoes off (Section 11.4.4).
Vital Signs	X		X	X	X	X	X		X	X	X	Collected after the subject has been at rest for at least 5 minutes (Section 11.5.3)

a All assessments will be performed before study drug dosing unless noted otherwise (Section 11). For any assessments with multiple time points for an individual visit, only 1 set of assessments will be collected if study drug is not administered on the day of the visit (i.e., study drug interruption or permanent discontinuation of study drug).

b The Safety Follow-up Visit is not required for subjects who complete the Week 24 Visit and enroll in the optional open-label extension safety study within 28 days after the last dose.

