#### Part B

- For subjects who complete the Treatment Period and enter an open-label extension safety study within 28 days of the Week 24 Visit: the Week 24 Visit
- For subjects who complete the Treatment Period and do not enter an open-label extension safety study within 28 days of the Week 24 Visit: the Safety Follow-up Visit
- For subjects who prematurely discontinue study drug treatment but do not withdraw consent (and assent, as applicable): the latest of the Week 24 Visit, ETT Visit, or Safety Follow-up Visit (if required)
- For subjects who withdraw consent or assent: date of withdrawal of consent or assent, whichever is earlier (Section 9.9)

If subjects are lost to follow-up (Section 9.1.5), the date of completion of study participation will be defined as the date of the last contact.

The end of study is defined in Section 13.2.8.

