##### **13.1.1.3 Documentation of Adverse Events**

All AEs will be collected from the time the ICF is signed until the subject completes study participation, as defined in Section 9.1.6.

All subjects will be queried, using nonleading questions, about the occurrence of AEs at each study visit. When possible, a constellation of signs and/or symptoms will be identified as 1 overall event or diagnosis. All AEs for enrolled subjects will be recorded in the CRF and source document. AEs for subjects who are screened but not subsequently enrolled in the study will be recorded only in the subject's source documents. The following data will be documented for each AE:

- Description of the event
- Classification of “serious” or “nonserious”
- Date of first occurrence and date of resolution (if applicable)
- Severity
- Causal relationship to study drug(s)
- Action taken
- Outcome
- Concomitant medication or other treatment given

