9.4 Safety Analysis

Part A and Part B

Safety is a secondary objective of Part A, and the primary objective of Part B. All safety analyses will be conducted for Part A and Part B separately, based on data from the corresponding TE period in the Safety Set.

The overall safety profile of study drug will be assessed in terms of the following safety and tolerability endpoints:

- Treatment-emergent adverse events (TEAEs)
- Clinical laboratory values
- Standard 12-lead ECGs
- Vital signs
- Pulse oximetry

Only descriptive analysis of safety will be performed, and no statistical testing will be performed.

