9.4.1 Adverse Events

Part A and Part B

For analysis purposes, AEs will be classified as pretreatment AEs, TEAEs, or post-treatment AEs, defined as follows:

- **Pretreatment AE:** any AE that occurred before the first dose date of study drug in the corresponding Part.

- **TEAE:** any AE that worsened (either in severity or seriousness) or that was newly developed at or after the first dose of study drug through the end of the TE period in the corresponding Part.
- **Extended TEAE: (Part B only)** any AE that worsened (either in severity or seriousness) or that was newly developed at or after the first dose of study drug in Part B through the end of the Extended Treatment-emergent Period.
- **Post-treatment AE:** any AE that worsened (either in severity or seriousness) or that was newly developed after the TE period in the corresponding Part.

For AEs with completely missing or partially missing start dates, if there is no clear evidence that the AEs were pretreatment or post-treatment, the AEs will be classified as TEAEs.

Details for imputing missing or partial start dates of adverse events are defined in [Appendix D](#).

An overview of all TEAEs will be provided with the following categories:

- Number of TEAEs (total number of TEAEs only)
- Subjects with any TEAEs
- Subjects with TEAEs by strongest relationship
- Subjects with TEAEs by maximum severity
- Subjects with TEAEs leading to study drug discontinuation (discontinuation of any study drug)
- Subjects with TEAEs leading to study drug interruption (interruption of any study drug)
- Subjects with grade 3/4 TEAEs
- Subjects with related TEAEs
- Subjects with serious TEAEs
- Subjects with related serious TEAEs
- Subjects with TEAEs leading to death

The following summary tables of TEAEs will be presented:

- All TEAEs
- TEAEs leading to treatment discontinuation
- TEAEs leading to treatment interruption
- Serious TEAEs
- TEAEs leading to death
- Grade 3/4 TEAEs
- TEAEs by strongest relationship
- TEAEs by maximum severity

- Related TEAEs
- Related serious TEAEs (Part B only)

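### SAP 9.1 sets completion of participation at the last unscheduled visit after Week 24 without a later-of clause, so the treatment-emergent period can end too early for subjects who do not roll over

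*SAP*

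**What the plan says.** SAP 9.1 runs the TE period from first dose "through 28 days after the last dose or the completion of study participation date in the corresponding Part, whichever occurs first". Protocol 12.3.1 has the same rule.

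The two documents differ on the completion date. Protocol 9.1.6 (Part B) fixes it, for subjects who complete treatment and "do not enter an open-label extension safety study within 28 days of the Week 24 Visit: the Safety Follow-up Visit". Table 3-4 times that visit: "Safety Follow-up Visit 28 (± 7) Days After the Last Dose of Study Drug". For subjects who stop drug early, 9.1.6 takes the latest of the Week 24, early termination and follow-up visits.

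SAP 9.1 refers to 9.1.6 only for subjects with no unscheduled visit after Week 24. For all others, "the completion of study participation is defined as the date of the last unscheduled visit".

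The TE period governs the safety analysis. SAP 9.4 makes all safety analyses "based on data from the corresponding TE period in the Safety Set". SAP 9.4.1 counts as post-treatment any event that worsened or was "newly developed after the TE period in the corresponding Part". SAP 9.1 uses unscheduled measurements "In the derivation of maximum and minimum values during TE periods", and SAP 9.4.2 counts laboratory threshold events within the TE period.

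**The concern.** The substitution was evidently meant to lengthen participation. Version 3.0 of the COVID-19 addendum allows unscheduled visits at any time, including after the last protocol visit, and SAP section 4 describes such visits as making up Week 24 assessments. For subjects who roll over, the sentence does lengthen participation, because their 9.1.6 date is the Week 24 Visit.

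For subjects who do not roll over, the 9.1.6 date is normally about four weeks later. A catch-up visit between Week 24 and follow-up then moves completion earlier, to before a visit the subject is still due to attend. The sentence is not limited to catch-up visits. A central-laboratory liver retest within 48 to 72 hours of a Week 24 finding (protocol 9.8.1) might also trigger it, although a local laboratory may do the retest and later monitoring may move the last visit.

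Collection does not stop at the SAP date. Protocol 13.1.1.3 says: "All AEs will be collected from the time the ICF is signed until the subject completes study participation, as defined in Section 9.1.6". Events in the gap are therefore recorded but classed as post-treatment. They drop out of the treatment-emergent tables, and safety values in the gap drop out of the TE maxima, minima and threshold counts. The split between concomitant and post-treatment medication (SAP 9.2.4) moves too. The Extended TE Period cannot recover these data, because it ends on the same completion date.

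**Working it through.** **Inputs**
- Week 24 target day: Day 169 (SAP Appendix A).
- Last dose L: the evening before the Week 24 Visit (protocol 9.6.1, Part B), so L = Day 168.
- Safety Follow-up S: L + 21 to L + 35 (Table 3-4), so Day 189 to 203.
- Last unscheduled visit after Week 24: U, a free value.

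**Check against the plan's own duration.** L + 28 = Day 196 = 28 weeks, and S spans 7 days either side. This reproduces the synopsis figure of 28 weeks ± 7 days.

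**Formulas for a completer who does not roll over**
- Protocol: TE end = min(L + 28, S). This is Day 189 if S = 189, and Day 196 if S is 196 or later.
- SAP: TE end = min(L + 28, U).
- With s = S − L and d = U − L, days lost = max(0, min(28, s) − d).

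In each pair below, the first figure is for follow-up at +21 days and the second for follow-up at +28 days or later.

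| U (Day) | d | SAP TE end | Days lost | Share of post-dose window (21 / 28 days) | Share of whole TE period (189 / 196 days) |
|---|---|---|---|---|---|
| 170 | 2 | 170 | 19 / 26 | 90.5% / 92.9% | 10.1% / 13.3% |
| 172 | 4 | 172 | 17 / 24 | 81.0% / 85.7% | 9.0% / 12.2% |
| 175 | 7 | 175 | 14 / 21 | 66.7% / 75.0% | 7.4% / 10.7% |
| 183 | 15 | 183 | 6 / 13 | 28.6% / 46.4% | 3.2% / 6.6% |

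The loss depends only on d and s, so it is the same for any Week 24 date in the ±5-day window. It is zero once d reaches 21 (follow-up at +21) or 28 (follow-up at +28 or later). If follow-up falls before Day 196 and U falls after follow-up, the SAP rule lengthens the TE period by up to 7 days. The Extended TE Period can lose up to 203 − 170 = 33 days.

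**Early discontinuers (Week 24 on Day 169).** If the last dose is on or before Day 141, L + 28 is at or before Day 169 and nothing is lost. With the last dose on Day 155 and U = 170, the protocol end is Day 176 to 183 and the loss is 6 to 13 days.

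**Effect on the chance of seeing an event.** For 45 subjects and 5% incidence, 1 − 0.95^45 = 0.9006; SAP Table 7-2 prints 90.0%. Assume a constant hazard with 5% incidence over Days 1 to 196, and cut k subjects to Day 170. Each cut subject then has p = 1 − 0.95^(170/196) = 0.0435. The chance of at least one event is 1 − 0.95^(45 − k) × (1 − 0.0435)^k:
- k = 0: 90.1%
- k = 1: 90.0%
- k = 5: 89.7%
- k = 10: 89.4%

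**The case against.** The strongest reply concerns weight. The Part B primary objective is safety through Week 24, and the rule acts only after Week 24. For completers every lost day is off drug.

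Several conditions must also coincide. The subject does not roll over, the last unscheduled visit precedes both follow-up and last dose plus 28 days, and an event or extreme value falls in between. Days 170 and 172 lie within the ±5-day Week 24 window, where a missed assessment could still be done on schedule, so the largest losses are the least natural cases. Safety is descriptive, all events remain in the listings, and serious events and deaths have a separate listing with a treatment-emergent flag (SAP 9.4.1).

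All of this stands as a limit on size. None of it supplies the missing later-of clause, and no other passage in either document does. The evident intent to extend is a reason to correct the sentence, because the rule as written will be programmed.

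One further point stands. The end-of-participation date also enters the compliance calculation (SAP 9.2.6), last-dose imputation (Appendix A) and adverse event end-date imputation (Appendix D). The correction should therefore be made to the completion date itself, not only to the TE end date.

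**Conclusion.** The concern holds. As written, SAP 9.1 can end the TE period before the date given by protocol 9.1.6 and the 28-day cap. This happens for any subject not rolling over whose last unscheduled visit after Week 24 precedes both of those dates, unless drug stopped at least 28 days before Week 24. Collected events are then misclassified as post-treatment, outside the primary safety tables.

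Per subject the loss is 6 to 13 days for a last unscheduled visit on Day 183 and 19 to 26 days on Day 170, given a last dose on Day 168 and follow-up within its window. Day 170 is the largest loss shown, not a typical one. The expected effect on the aggregate tables is small, and the probabilities above rest on an assumed constant hazard and assumed numbers of affected subjects. The documents do not show how many subjects, if any, are affected.

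Whether by-visit follow-up summaries also lose values is unclear, because Appendix A assigns that visit by its nominal label. The point should be fixed because it bears on the primary endpoint's window and costs almost nothing to correct.

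**What to change.** Replace the sentence in SAP 9.1 with: *If a subject has any unscheduled visit after Week 24, participation is complete on the later of two dates: the one given by CSP Section 9.1.6 and the date of the last such visit.*

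For a completer with U = Day 176, the TE period then ends on Day 189 if follow-up is on Day 189, and on Day 196 if follow-up is on Day 196 or 203. These are the protocol dates; the present text gives Day 176. The extension for late catch-up visits is kept, and subjects who roll over are treated as now.

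The cost is one sentence and a maximum of two dates in the completion-date derivation, so that the TE period, the Extended TE Period, compliance and the imputation rules all use the same date. No new data are needed.

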9.2 Background Characteristics

9.2.1 Subject Disposition

Part A and Part B

The number of subjects in the following categories will be summarized based on the All Subjects Set:

- All Subjects Set
- Safety Set
- FAS

The number and percentage (based on FAS) of subjects in each of the following disposition categories will be summarized:

- Completed treatment
- Prematurely discontinued treatment and the reason for discontinuation
- Completed study
- Prematurely discontinued the study and the reason for discontinuation
- Rollover to open-label study (Part B only)

A listing will be provided for subjects who discontinued treatment or who discontinued study with reasons for discontinuation.

9.2.2 Demographics and Baseline Characteristics

Part A and Part B

Demographics and baseline characteristics will be summarized based on the FAS.

Demographic data will include the following:

- Age at baseline (in years)
- Sex (male, female)
- Ethnicity (Hispanic or Latino, not Hispanic or Latino, and not collected per local regulations)

- Race (White, Black or African American, Asian, American Indian or Alaska Native, Native Hawaiian or Other Pacific Islander, Other, and not collected per local regulations)
- Geographic region (North America for Part A; North America, Europe [including Australia] for Part B)

Baseline characteristics will include the following:

- CFTR genotype group (F/F, F/MF)
- Weight group (<30 kg, and ≥ 30 kg)
- Weight (kg)
- Weight z-score
- Height (cm)
- Height z-score
- BMI (kg/m^2)
- BMI z-score

Disease characteristics will include the following:

- ppFEV₁ at baseline (<70, ≥ 70 to ≤ 90 , and >90)
- ppFEV₁ at baseline (continuous)
- Sweat chloride at baseline (continuous)

For Part B, the following additional disease characteristics will also be provided:

- CFQ-R respiratory domain score at baseline (child's version; continuous)
- LCI_{2.5} at baseline (continuous)
- Prior use of CFTR modulator (Yes, No)
- Prior use of dornase alfa (Yes, No)
- Prior use of azithromycin (Yes, No)
- Prior use of inhaled antibiotic (Yes, No)
- Prior use of any bronchodilator (Yes, No)
- Prior use of any inhaled bronchodilator (Yes, No)
- Prior use of any inhaled hypertonic saline (Yes, No)
- Infection with *Pseudomonas aeruginosa* within 2 years prior to screening (Positive, Negative)

In addition, the following data listings will also be provided:

- Informed consent/assent;
- Inclusion/Exclusion criteria violation for subjects with any such violations.

